- 4.0% of participants had elevated antibodies to the EBOV at baseline. An elevated baseline antibody level in PREVAIL I was defined using the distribution of antibody levels measured from sera collected in 2004 and 2001 from 92 adults in Mali, a region where there had been no reports of ZEBOV transmission or disease during this time period. Baseline antibody levels were considered elevated in PREVAIL I if they were greater than 3 standard deviations (SD) above the mean (607 enzyme-linked immunosorbent assay units/mL based on the FANG ELISA assay).
- Among participants without elevated antibodies at baseline (96%), the percent with an antibody response at week 1 was 2.5% for those given the rVSVΔG-ZEBOV-GP vaccine and 1.5% for those given placebo (p=0.36). By month 1 antibody levels had increased substantially and 83.7% of participants given the rVSVΔG-ZEBOV-GP vaccine had an antibody response as compared to 2.8% of placebo participants (p<0.001). At 12 months, 79.5% of participants given the rVSVΔG-ZEBOV-GP vaccine had an antibody response versus 6.8% of participants in the placebo group (p<0.001). Responders during follow-up were defined as having a change in log-transformed antibody levels greater than 2 SD of the change in the placebo group at month 1.

With type 1 error = 0.0167 (2-sided) to adjust for the three comparisons, separately for adults and for children in all age groups combined, and power = 0.90, even if the percent with a positive antibody response at 12 months is 50% in a vaccine group, with equal allocation, approximately 30 participants per group (60 participants total) are needed assuming the percent in the placebo group with a positive antibody response is approximately 7%. With unequal allocation as for the rVSVΔG-ZEBOV-GP with the booster versus placebo comparison, a total of 63 participants (21 vaccinated with rVSVΔG-ZEBOV-GP with a boost and 42 vaccinated with placebo), a difference of 50% versus 7% can also be detected at 12 months with 87% power. These sample size estimates indicate that power for the planned subgroup analysis by age is also appropriate.

The planned sample size is also adequate for the comparisons with placebo if more than 4% of participants are antibody positive at baseline and excluded from the primary analysis, and if there is some missing data 12 months.

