If a correlate of protection is identified, the vaccine strategies will be compared with one another at multiple time points. For the contrast with the smallest sample size (200 adults or children assigned rVSVΔG-ZEBOV-GP with a boost versus 400 vaccinated with rHAd26/MVA or rVSVΔG-ZEBOV-GP without a boost), power is 0.83 to detect an absolute difference of 15% in the antibody response (50% versus 35%) at the 0.0167 (2-sided) level of significance, assuming 10% of participants are excluded due to a positive antibody level at entry or for missing data. If the percent with a positive antibody response at 12 months is 75%, power is 0.87 to detect a 15% lower antibody response for this planned contrast.

For SAEs, we estimate that 5% of participants in the placebo group will experience an SAE by 12 months. This estimate is based on data from PREVAIL I where after 12 months of follow-up 11.8% of participants assigned to placebo developed an SAE. In PREVAIL I most of the SAEs were due to malaria events which did not require hospitalization. Thus, with the exclusion of laboratory confirmed malaria events that did not require hospitalization, the 12 month percent with SAEs in this study is expected to be lower. Among adults and children, considered separately, with type 1 error = 0.0167 (2-sided), power is 0.88 to detect an increase of 7% (to 12%) for the rHAd26/MVA and for the rVSVΔG-ZEBOV-GP without a boost strategies compared to placebo assuming 400 per group. For the rVSVΔG-ZEBOV-GP with a boost (N=200) versus placebo (N=400) comparison for adults and children, power is 0.86 to detect an increase of 9% (to 14%).

Sample size is also sufficient for comparing the vaccine strategies with the pooled placebo group for the antibody response at day 14 (an important secondary objective that address the immediacy of the immune response). For example, if the antibody response at 14 days is 25% in a vaccine group and 7% in the placebo group, fewer than 250 participants total are needed.

A sample size re-estimation will be performed before enrolment has been completed to ensure there is adequate power for both adults and children to address the primary objectives.

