Prior to carrying out the endpoint analyses which pool the two placebo groups, the two placebo groups will be compared for the immunogenicity and safety outcomes. The primary analyses for adult and children will be carried out at the 0.0167 (2-sided) level of significance and will compare the three vaccine strategies with the pooled placebo group for the percent with a positive antibody response at 12 months. Each pair-wise comparison will be carried out using Mantel-Haenszel chi-square statistics which consider stratification by vaccination center. Similar methods will also be used to compare groups for the immediacy of the antibody response at 14 days. These analyses will exclude those participants with elevated antibody levels at baseline. Participants will not be screened at study entry for elevated antibody levels. These exclusions will be carried out during analysis. Analyses will also be carried out for all randomized participants irrespective of antibody level at baseline.

Similar methods will be used to compare antibody responses of each vaccine strategy with the pooled placebo group at other time points, including 28 days after randomization and 28 days following the booster vaccination. The two additional primary objectives for immune responses, pooled rVSVΔG-ZEBOV-GP groups versus pooled placebo groups 28 days after randomization for Merck, and rHAd26/MVA versus pooled placebo groups approximately 28 days following

booster vaccination for Janssen, will be carried out the 0.05 (2-sided) level of significance.

All comparisons (for adults, children, and for adults and children combined) of immune responses and safety outcomes at other time points will be carried out at the 0.0167 (2-sided) level of significance when there are three pair-wise comparisons made (e.g., each vaccine strategy versus pooled placebo) and at the 0.025 (2-sided) level of significance when there are two pair-wise comparisons made (e.g., for comparisons at days 7, 14, 28 and 56 with the pooled placebo group in which the two rVSVΔG-ZEBOV-GP strategies are pooled).

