#### 2.1.4 Immunogenicity outcomes

The primary endpoint specified in the protocol by the PREVAC group is the percentage of antibody responders at 12 months. An antibody responder at 12 months is defined as a participant who experiences a 4-fold increase in antibody level from baseline (i.e., a .6 increase on the  $\log_{10}$  scale) and for whom the antibody level at 12 months is  $\geq 200$  EU/mL. With this definition, participants with a missing baseline or 12 month result will be excluded. Also, with this definition, there will be no exclusion of participants with elevated antibody levels at entry.

Each of the 3 vaccine strategies will be compared with the pooled placebo group at the 0.0167 (2-sided) level of significance. Analyses will be carried out for adults and children separately and combined.

This same definition will be used for defining responders at 7, 14, 28, 56, and 63 days and at 3 and 6 months. For the comparisons with the pooled placebo group at 7, 14, 28, and 56 days, the two rVSV strategies will be combined. The two pair-wise comparisons at these time-points, each vaccine strategy versus pooled placebo, will be carried out at the 0.025 (2-sided) level of significance.

As a sensitivity analysis, for the above analyses based on responders, participants with an antibody level  $\geq 200$  EU/mL at baseline will be excluded.

The following additional summaries of antibody levels will be carried out, separately for children and adults:

- Geometric mean titers at 7, 14, 28, 56, and 63 days, and 3, 6 and 12 months separately for adults and children. Comparison groups will be defined as above for version 4.0 participants at day 63 and months 3 and 6. For 7, 14, 28, and 56 days, the rVSV vaccine groups with and without the boost will be combined. Analysis of covariance with stratification by site and with baseline  $\log_{10}$  antibody level as a covariate will be used to compare each vaccine group versus the pooled placebo for  $\log_{10}$  antibody levels at each follow-up visit (geometric mean ratios will be cited).
- Fold increase from baseline to 14 and 28 days, and 6 and 12 months (<2, 2 to < 4, 4 to < 8, 8 to <16,  $\geq 16$ ).
- Box plots of antibody levels at 14 and 28 days, and 6 and 12 months. For days 14 and 28 the rVSV vaccine groups with and without the boost will be combined.

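### The fixed 0.0167 and 0.025 levels are valid, but Holm's step-down gives more power at the same 5% family error when more than one comparison in a family has a real effect

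*Protocol*

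**What the plan says.** Protocol 2.7 gives the reason for the level: "With type 1 error = 0.0167 (2-sided) to adjust for the three comparisons". Protocol 7.1 extends it beyond the primary endpoint. Comparisons of immune responses and safety outcomes at other time points are made "at the 0.0167 (2-sided) level of significance when there are three pair-wise comparisons made", and at 0.025 when there are two. SAP 2.1.4 repeats the rule for 12-month responders: "Each of the 3 vaccine strategies will be compared with the pooled placebo group at the 0.0167 (2-sided) level of significance". It uses 0.025 at 7, 14, 28 and 56 days, where the two rVSV groups are combined.

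The same level underlies two sets of power figures in protocol 2.7:
- **SAEs.** "we estimate that 5% of participants in the placebo group will experience an SAE by 12 months". "Among adults and children, considered separately, with type 1 error = 0.0167 (2-sided), power is 0.88 to detect an increase of 7" percentage points (to 12%), "compared to placebo assuming 400 per group". Power is 0.86 for 14% v 5% with 200 v 400.
- **Strategy against strategy, if a correlate of protection is found.** "power is 0.83 to detect an absolute difference of 15% in the antibody response (50% versus 35%) at the 0.0167 (2-sided) level of significance", with 10% of participants excluded, and 0.87 from a base of 75%.

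Neither document describes a step-down, closed or hierarchical procedure. SAP 2.1.5 gives Mantel-Haenszel p-values for SAEs without any significance level, so the level for safety comes from protocol 7.1. The strategy contrasts are exploratory objectives (protocol 2.5) and do not appear in the SAP.

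**The concern.** Dividing 0.05 equally and holding every comparison to its share is the Bonferroni rule. The documents do not use that name or state a 5% family error; both are inferred from 0.05/3 and the stated reason for it. Once one null hypothesis in the family has been rejected, fewer can still be true, and the remaining comparisons need not be held to 0.05/3. The fixed rule ignores this and so gives up some power.

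The 12-month antibody comparisons have power near 1 under any rule. The loss can matter only where stated power is limited: the SAE comparisons (0.86 to 0.88) and the later strategy contrasts (0.83 to 0.87). Protocol 2.7 gives those contrasts as a reason for enrolling more participants than the primary objectives require.

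**Working it through.** **1. Reproduce the stated power.** Inputs are from protocol 2.7. With p̄ the simple average of the two proportions and d their difference:

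SE0 = √[p̄(1−p̄)(1/n1+1/n2)], SE1 = √[p1(1−p1)/n1 + p2(1−p2)/n2], power = Φ[(d − z·SE0)/SE1], with z = 2.393 for 0.0167 two-sided.

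SAE, 5% v 12%, 400 v 400: p̄ = 0.085, SE0 = 0.01972, SE1 = 0.01956. (0.07 − 2.393 × 0.01972)/0.01956 = 1.166, so power is 0.878.

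| Comparison | Groups | Computed | Stated |
|---|---|---|---|
| SAE 5% v 12% | 400 v 400 | 0.878 | 0.88 |
| SAE 5% v 14% | 400 v 200 | 0.862 | 0.86 |
| Strategy 50% v 35% | 360 v 180 | 0.829 | 0.83 |
| Strategy 75% v 60% | 360 v 180 | 0.866 | 0.87 |

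All four reproduce. If p̄ is weighted by group size, the second row becomes 0.896, so that figure is sensitive to the approximation.

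**2. The step-down rules.** Order the p-values from smallest to largest.
- Holm, family of three: test at 0.05/3 = 0.0167, then 0.05/2 = 0.025, then 0.05, stopping at the first failure. Family of two: 0.025, then 0.05.
- Holm controls family error under any dependence, which covers the shared placebo group. Its first step is the fixed rule's threshold, so the chance of at least one rejection is identical.
- For 12% v 5% with 400 per group, the formula in step 1 gives power 0.878 at 0.0167, 0.906 at 0.025 and 0.946 at 0.05. Holm power lies between the first and last, depending on the other comparisons.

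**3. SAE simulation.** 500,000 trials per pattern, 400, 400 and 200 vaccinated v 400 on a shared placebo at 5%, unstratified pooled z-tests, no continuity correction. Power for 12% v 5%, 400 per group:

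| True SAE rates (rHAd26/MVA, rVSV, rVSV with boost) | Fixed 0.0167 | Holm |
|---|---|---|
| 12%, 5%, 5% | 0.887 | 0.888 |
| 12%, 12%, 5% | 0.887 | 0.908 |
| 5%, 12%, 14% | 0.888 | 0.912 |
| 12%, 12%, 14% | 0.887 | 0.938 |

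In the last pattern the boosted arm goes from 0.909 to 0.947, and the chance of finding all three from 0.761 to 0.880. The chance of at least one rejection is 0.988 under both rules. With a continuity correction the levels fall but the pattern holds: 0.864 to 0.917 per comparison, and 0.715 to 0.842 for all three.

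Family error with no effect is 0.043 under both rules. With two true effects, Holm falsely rejects the one true null 0.042 to 0.044 of the time.

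**4. Primary endpoint.** At 50% v 7% with 180 v 360 (10% loss), power is 1.00 at 0.0167. There is nothing to gain.

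**5. Strategy contrasts.** With three arms and three pairwise contrasts, if one null is false at most one of the other two can be true. Shaffer's rule therefore tests the smallest p at 0.0167 and the other two at 0.05. With 360, 360 and 180 participants and the boosted arm differing from both others, power per boosted-arm contrast is:

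| Rates | Fixed | Holm | Shaffer |
|---|---|---|---|
| 50%, 50%, 35% | 0.823 | 0.849 | 0.877 |
| 75%, 75%, 60% | 0.878 | 0.898 | 0.920 |

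Family error with Shaffer is 0.042 with no effect and 0.048 to 0.049 with one true null in these two patterns. In the other patterns run it reached 0.050.

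**The case against.** A fixed 0.05/3 is prespecified, simple and valid, and no primary conclusion can turn on it. That stands: this is lost efficiency, not an error.

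Protocol 2.7 powers each SAE comparison on its own and gives no joint pattern of effects. The rise from 0.76 to 0.88 needs all three strategies to raise SAEs together. That also stands; with one effect the gain is about 0.1 percentage point. For the boosted arm, the difference between stated power (0.86) and simulated power under the fixed rule (0.91) is about as large as the Holm gain.

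A reader might infer that the plan will miss SAE excesses. The documents do not support this. SAP 2.1.5.1 reports counts, percentages with 95% intervals, p-values without a cut-off and time-to-event analyses, and SAP 2.1.5.2 adds line listings. In protocol 4.5.1 and 7.2 the DSMB acts on severity, relatedness and frequency, not on 0.0167. A p-value of 0.03 would be reported under either rule; only its formal label differs.

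The strategy contrasts depend on a correlate being found, and their 0.0167 level is explicit only as a sample-size input. Protocol 7.2 already provides for updating the SAP in that event. That limits the point's reach, and sets when the rule for those contrasts can be written.

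**Conclusion.** The point holds as an optional improvement in efficiency. Holm is never less powerful than the fixed levels at the same family error, and the documents contain no step-down rule. For SAEs at the protocol's rates the gain per comparison is about 0.1 percentage point with one true effect, 2 with two, and 4 to 5 with all three. For strategy contrasts, Shaffer's rule adds 4 to 5 points if the boosted arm differs from both others. The chance of at least one rejection and the 12-month antibody result do not change.

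It would be wrong to read this as a fault in type 1 error control, an underpowered trial or a threat to the primary result: 0.0167 is conservative and the stated power figures reproduce. The sizes rest on assumed joint effect patterns and on unstratified tests, whereas the plan stratifies by vaccination center.

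**What to change.** Before unblinding:
- In SAP 2.1.4, replace the fixed levels with Holm within each family: 0.0167, 0.025, 0.05 for three comparisons; 0.025, 0.05 for two.
- In SAP 2.1.5, add the same rule for SAE and other safety comparisons. There is no level there to replace.
- Align protocol 7.1 at the next amendment. Protocol 8.1 requires ethics committee approval for amendments, so one need not be raised for this alone.
- Keep the power figures in protocol 2.7 as minimums.

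If a correlate of protection is found and the SAP is updated, specify Shaffer's step-down (0.0167, then 0.05 and 0.05) for the three strategy contrasts at 3 and 12 months. It does not apply at 14 or 28 days, where the rVSV groups are pooled and only one contrast remains.

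The cost is wording and one real disadvantage. Each threshold then depends on the other p-values in its family, and step-down tests have no simple matching confidence intervals, whereas a fixed 0.0167 corresponds to a 98.3% interval. The SAP plans no 98.3% intervals. Its 95% intervals are for SAE percentages and subgroup ratios, and it states no interval level for the main responder comparison, so it should say which level will be reported.

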## **2.8. Study cohort**

This phase 2 study will be conducted in Guinea, Liberia, Mali, and Sierra Leone.

As part of the public health campaign to prevent EVD, there will be widespread communication about the trial to encourage volunteers to go to a vaccination center near where they live.

Our goal is to include 1,400 adults and 1,400 children. The gender and age distributions of those enrolled will be closely monitored. The steering committee may request that more men or women or participants in specific age groups be enrolled to ensure broad generalizability of the findings.

Eligibility for enrolment in the trial will be assessed on a first-come first-serve basis; in case of oversubscription we will ensure that access is made on an equitable basis that does not compromise the external validity of the trial.

### **2.8.1. Inclusion criteria**

The inclusion criteria for the study are broad reflecting the target population that would eventually receive efficacious vaccines.

- Informed consent/assent
- Age  $\geq$  1 year
- Planned residency in the area of the study site for the next 12 months
- Willingness to comply with the protocol requirements

### **2.8.2. Exclusion criteria**

- Fever  $>$  38° Celsius
- History of EVD (self-report)
- Pregnancy (a negative urine pregnancy test is required for females of child-bearing potential, i.e., females who have experienced menarche or who are aged 14 years and older)
- Positive HIV test for participants  $<$  18 years of age
- Reported current breast-feeding
- Prior vaccination against Ebola (self-report)
- Any vaccination in the past 28 days or planned within the 28 days after randomization (initial vaccination)
- In the judgement of the clinician, any clinically significant acute/chronic condition that would limit the ability of the participant to meet the requirements of the study protocol

## **2.9. Randomization and blinding**

Eligible participants will be randomized in a 2:1:2:1:1 allocation to rHAd26/MVA (prime and boost), 0.5 mL of placebo (prime and boost), rVSV $\Delta$ G-ZEBOV-GP without a boost, rVSV $\Delta$ G-ZEBOV-GP with a boost, or, 1mL of placebo (prime and boost) (Figure 1). Syringes will be pre-labelled with a unique SID number according to a centrally prepared randomization schedule. The tear-off label will also include a bar code identifier. For each vaccination center, the randomization schedule will be prepared using block randomization to ensure the desired allocation ratio for the five arms of the study for each vaccination center.

It is possible that the person carrying out the vaccination will be able to differentiate syringes by the fill volume. The rVSV $\Delta$ G-ZEBOV-GP vaccine has a 1 mL fill volume and the rHAd26/MVA vaccines have a 0.5 mL fill volume. The person carrying out the vaccination will not know whether vaccine or matched placebo is given.

At the time of vaccination, a tear-off label on the syringe that includes the SID will be attached to the baseline CRF (or an eCRF will be used). This will be the primary

link used between the vaccine administered and the PID, and PIDs associated with SIDs will be available to the pharmacy.

With this approach, randomization does not occur until the participant is vaccinated with the prime vaccine.

Participants randomized to the rVSVΔG-ZEBOV-GP vaccine without a boost for the initial vaccination will receive placebo (1.0 mL fill) at 56 days. Those randomized to receive rHAd26/MVA initially will receive the MVA-BN-Filo boost at 56 days in a syringe with a 0.5 mL fill; and those randomized to rVSVΔG-ZEBOV-GP with a boost will receive the rVSVΔG-ZEBOV-GP vaccine again at 56 days in a syringe with a 1 mL fill. Two groups will receive placebo (saline) for the prime and booster vaccination. For one group, a 0.5 mL fill syringe will be prepared for each vaccination and for the other a 1.0 mL fill syringe will be prepared for each vaccination. The syringe used at 56 days will be labeled with the volunteer's PID.

Study participants and clinical staff assessing the study participants for safety and laboratory outcomes will be fully blinded until all participants complete 12 months of follow-up. The laboratories carrying out the safety and immunogenicity analyses will be blinded to the vaccine assignment. Procedures will be put into place to break the blind if necessitated by a medical emergency. If unblinding of a participant for safety reasons is required, it will be documented.

After 12 month follow-up visits have been completed for all participants, the study will be unblinded. Follow-up may continue through 5 years if funding permits.

### **3. STUDY PLAN**

Vaccination centers will be established in West Africa to consent, vaccinate and follow study participants. A CRF with a unique PID will be completed for each participant consented and screened. The CRF may be paper or an eCRF. The procedures described in this protocol are in terms of a paper CRF. If an eCRF is used, the procedures described will be adapted for their use.

At the time of vaccination, study volunteers will be given an identification card that identifies them as a study participant. The identification card will include contact information in the event they experience vaccine side effects, or signs and symptoms of Ebola. Volunteers will be encouraged to contact the vaccination center by telephone at any time of day if they have any AEs. If the participant experiences an AE requiring immediate attention, they will be given instructions on which hospital to go to for evaluation and treatment.

Women of childbearing potential will be told to use adequate birth control measures for at least 3 months following the initial vaccination and booster vaccination. Men who are sexually active with women of child-bearing potential will be told to use condoms for at least 3 months following the initial vaccination and booster vaccination. Participants will also be instructed to avoid sharing items during the period of potential virus shedding.

Following randomization, all participants will be seen at 7, 14, 28, 56 and 63 days, and at 3, 6 and 12 months. After 12 months, participants will be seen annually if funding permits. In addition to these study visits, volunteers will be encouraged to contact the vaccination center by telephone if they experience AEs.

